## **12.6 Resources Available**

1. Members of the study team, as well as staff nurses, fellows and other clinic staff may be present during study procedures.
2. The PI, the Co-I or the study coordinator will give the subjects information about when they will receive the study drug(s), as well as ensure the study drug is ordered. The PI, the Co-I or the study coordinator/research nurse will give the subjects information about how to take the study drug (s).

Any procedures that are commonly performed by phlebotomists, technicians, and nurses as part of standard clinical practice will be done by these clinical staff, regardless of whether the tests are being done

solely for research purposes. Assessments such as physical exams will only be done by study investigators. Any questionnaires or other patient materials that may be generated will be given and explained to the subject by study staff.

3. Research procedures will take place within the hospital. Crash carts and other emergency interventions will be immediately available. Tufts Medical Center's emergency department (located within the same building complex as the location where study procedures occur) is verified by the American College of Surgeons and designated by the Massachusetts Department of Public Health as a Level I Adult and Pediatric Trauma Center.

### **12.7 Subject Compensation for Participating in the Study**

Subject and their caregivers will be provided with travel services on a case by case basis by a company called ClinEdge. ClinEdge will also arrange for the reimbursement for reasonable out of pocket costs for mileage (up to \$.55 per mile for personal vehicle travel cost. The total amount reimbursed will be equal to the total mileage traveled), meals (up to \$37 per day for the subject and \$37 per day for a caregiver), and other incidentals (like parking or taxi fares to and from the hospital) that they spend for each study visit. The study coordinator will provide subjects with an information packet containing the necessary forms, guidelines and instructions for using this travel service. Subject will need to bring all the receipts for any of these expenses in order to reimbursed for them. In order to provide this travel service for subjects, ClinEdge must have access to personal information of travelers, including name and address, however, this personal information will be used by ClinEdge only as needed to make these travel arrangements.

There are no plans to provide financial compensation to subjects for any knowledge or understanding of AL amyloidosis that is gained from testing or analysis of their bodily fluids and tissue samples collected during the study.

### **12.8 Subject Compensation for Adverse Effects on Health**

The Sponsor or its designee will adhere to local regulations regarding clinical trial compensation guidelines to subjects whose health is adversely affected by taking part in the study.

### **12.9 Protocol Amendments and Study Termination**

Protocol amendments and amendment to the Informed Consent must be made only with the prior approval of the Sponsor and/or its designee. The IRB/IEC must be informed of and approve all protocol amendments. The Investigator must send a copy of the approval letter from the IRB/IEC to the Sponsor and/or designee.

Both the Sponsor and the Investigator reserve the right to terminate the study according to the study contract. The Investigator should notify the IRB/IEC in writing of the trial's completion or early termination and send a copy of the notification to the Sponsor and/or designee.

### **12.10 Finance, Insurance, and Indemnity**

A study center will not initiate study participation until a fully executed Clinical Study Agreement is in place between the study center and the Sponsor. All details associated with finance, insurance, and indemnity are delineated in the Clinical Study Agreement.

### **12.11 Publication Policy**

All publication rights are delineated in the Clinical Study Agreement.

## 14 APPENDICES

### Appendix 1 For Stratification

#### Hematologic Response and Progression Criteria

Response Subcategory	Response Criteria
Complete Response (CR)	
 
Normalization of free light chain levels and ratio, negative serum and urine immunofixation
 

Very Good Partial Response (VGPR)*	
 
Reduction in the dFLC to <40 mg/L
 

Partial Response (PR)*	
 
A greater than 50% reduction in the dFLC
 

No Response (NR)	
 
Less than a PR
 

	
 
From CR: any detectable monoclonal protein or abnormal free light chain ratio (light chain must double)
 

Progression	
 
From PR, 50% increase in serum M protein to > 0.5 g/dL or 50% increase in urine M protein to > 200 mg/day (a visible peak must be present) or free light chain increase of 50% to > 10 mg/dL (100 mg/L)
 

Abbreviations: dFLC = difference between involved and unininvolved free light chains. \*Only applicable for subjects with dFLC > 50 mg/L (5 mg/dL) at study entry.

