## RAIN PROTOCOL SYNOPSIS

Title	RAIN (Renal AL-amyloid Involvement and NEOD001): A Multicenter Randomized Double-blind Phase 2b Study of NEOD001 in Previously Treated Subjects with Systemic Light-chain (AL) Amyloidosis and Persistent Renal Involvement
Phase	2b
Planned Number of Study Centers	9 centers in the USA
Objective	The objective of this study is to determine if the investigational agent NEOD001, a monoclonal antibody that targets a light chain amyloid epitope, increases the frequency of confirmed renal responses (see Appendix 1) in previously treated patients with AL and renal involvement who have responded to prior treatment with a maintained complete, very good partial or partial hematologic response (CR, VGPR, PR) and do not need chemotherapy for their hematologic disease.
Study Design	
This is a multicenter, Phase 2b, randomized, double-blind, placebo-controlled, two-arm, parallel-group efficacy and safety study of NEOD001 as a single agent administered intravenously in adults with AL amyloidosis who have a maintained hematologic response (Appendix 1) to their most recent treatment for AL amyloidosis (e.g., chemotherapy, autologous stem cell transplant [SCT]) and have persistent renal dysfunction.
 
Subject screening will occur during the 28 days prior to the first administration of study drug (i.e. month 1 day 1). If screening assessments are completed and all eligibility requirements are met, the subject will be enrolled. Screening assessments are listed in Table 1.
 
Study visits will occur every 28 days based on scheduling from month 1 day 1. A <math>\pm</math>5-day window is allowed for visits starting after month 1. Subjects may receive up to 12 infusions of study drug. Subjects who discontinue study drug before the initial End of Study (EOS) visit should have an Early Treatment Discontinuation (ETD) Visit 30 (<math>\pm</math>5) days after their final administration of study drug.
 
After completing 12 months of treatment and the confirmatory EOS visit, a subject may enter an open-label extension (OLE) study, during which subjects will receive active treatment with NEOD001 for 12 months and may receive concurrent chemotherapy.

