Number of Subjects and Cohort Specifications	50 subjects randomized to NEOD001 and 50 subjects randomized to placebo. The randomization will be stratified (Appendix 1) according to: 
 
• Complete response/very good partial response (CR/VGPR) vs partial response (PR) to most recent line of therapy
 
• Renal stages 1 or 2 vs renal stage 3
 

Study Drug, Dose, and Mode of Administration	
Study drug consists of NEOD001 24 mg/kg (dose not to exceed 2500 mg) or placebo.
 
Study drug will be administered once every 28 (<math>\pm</math>5) days; a minimum

	
of 21 days between doses is required. Subjects may receive up to 12 infusions of study drug.
 
Study drug will be administered in a 250 mL bag as an initial 120 (<math>\pm 10</math>)-minute intravenous (IV) infusion. If, in the opinion of the Investigator, the subject tolerates the initial infusion, subsequent infusions may be administered over 60 (<math>\pm 10</math>) minutes. The length of the infusion may be extended over a longer period of time if and when it is clinically indicated. If the infusion must be extended beyond 4 hours, the study drug should be split into two 125-mL bags to ensure that the study drug will not remain at room temperature for longer than 4 hours (i.e. the second bag should remain refrigerated until ready for use). If an infusion-related reaction occurs, follow instructions in Section 5.3.2.
 
Subjects should be closely monitored for 90 (<math>\pm 10</math>) minutes following completion of the study drug infusion. The Investigator may increase this standard monitoring time if deemed appropriate or per local standards. In the event of any clinical concerns or suspicious signs or symptoms after the infusion, the subject will remain under observation for as long as the Investigator deems it appropriate

Control Group	Normal saline will be used as the placebo control.

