## **4.0 SELECTION, DISCONTINUATION, AND WITHDRAWAL OF SUBJECTS**

### **4.1 Inclusion Criteria**

Subjects must meet **all** of the following criteria:

1. 18 years of age or older
2. Biopsy-proven diagnosis of AL amyloidosis by immunohistochemistry or mass spectroscopy of a tissue biopsy excluding bone marrow
3. Screening renal biopsy for RAIN confirming AL amyloidosis as exclusive or dominant cause of renal damage
4. Persistent renal involvement with proteinuria (predominantly albumin) > 500mg/day in a 24-hour urine collection
5. CKD 1, 2 or 3
6. ≥1 prior systemic hematologic therapy for free light chain (FLC) producing hematologic malignancy underlying the initial diagnosis of AL amyloidosis with a FLC response to treatment (PR, VGPR, CR) that is deemed stable and not requiring further treatment
7. ECOG Performance Status ≤ 2
8. Clinical laboratory values:
  - Absolute neutrophil count > 1000/µL
  - Platelet count > 75,000/µL
  - Total bilirubin ≤ 1.5X ULN
  - Alkaline phosphatase ≤ 5X ULN
  - ALT or AST ≤ 3X ULN
  - NT-proBNP < 1800 pg/mL
9. Voluntary written consent must be given before performance of any study-related procedure not part of standard medical care with the understanding that consent may be withdrawn by the patient at any time without prejudice to future medical care.

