## 8.3 Analysis of Efficacy Endpoints

### 8.3.1 Primary Efficacy Analysis

This stratified randomized double-blind phase 2b study has as its primary efficacy endpoint confirmed renal response at the confirmatory EOS visit to evaluate 12 months of study treatment. The primary efficacy analysis will test the following hypotheses:

- $H_0$ : The confirmed renal response rate after 12 months of treatment is equal between placebo and NEOD001.
- $H_1$ : The confirmed renal response rate after 12 months of treatment is different between placebo and NEOD001.

The primary efficacy analysis of the confirmed renal response rates after 12 months of treatment with NEOD001 or placebo will be performed with the Mantel-Haenszel (MH) test at the alpha=0.05 (two-sided) level of significance. The analysis will be stratified by the randomization stratification variables. The number and percentage, with associated 95% exact confidence intervals (CI) of subjects in each category of response will be presented by treatment group. The proportional treatment difference with associated exact 95% CI will be presented.

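### Appendix 1 limits VGPR and PR to patients with dFLC above 50 mg/L at study entry, so a maintained VGPR, or a PR entering at 50 mg/L or less, cannot be classified for stratification

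*Combined protocol and SAP*

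**What the plan says.** Appendix 1, which is headed as being for stratification, gives three response categories:

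- CR: "Normalization of free light chain levels and ratio, negative serum and urine immunofixation".
- VGPR: "Reduction in the dFLC to" below 40 mg/L.
- PR: "A greater than 50% reduction in the dFLC".

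VGPR and PR carry an asterisk and CR does not. The asterisk reads: "Only applicable for subjects with dFLC > 50 mg/L (5 mg/dL) at study entry".

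The synopsis (Number of Subjects and Cohort Specifications) gives the randomization factor two levels: "Complete response/very good partial response (CR/VGPR) vs partial response (PR) to most recent line of therapy". Section 3.4.1 uses the same two levels and cites Appendix 1, but refers only to response to therapy, without saying which line. Section 8.3.1 carries the factor into the primary test: "The analysis will be stratified by the randomization stratification variables".

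On who enters, the synopsis describes adults "who have a maintained hematologic response (Appendix 1) to their most recent treatment for AL amyloidosis". Section 4.1, criterion 6, requires prior therapy "with a FLC response to treatment (PR, VGPR, CR) that is deemed stable and not requiring further treatment". Section 4.2, criterion 3, excludes chemotherapy within 6 months, or SCT within 12 months, of the first dose.

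**The concern.** The footnote would make sense in a trial of initial therapy, where dFLC at entry is the value from which the response is measured. In RAIN the response comes first and entry follows. The dFLC at entry is the value after response, so the footnote asks for a high value at the point where VGPR requires a low one.

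The same table feeds a randomization factor and the strata of the primary test. If the written rule cannot place a patient, someone must choose a stratum by a convention that is not written down. With 9 centers, that convention could vary between readers or over time. The hematologic factor would then give less of the balance and precision it was included for.

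**Working it through.** **The plan's own figure.** Section 8.5 assumes 55% vs 25%, two-sided alpha 0.05, power 0.80 and 18% drop-out, using a chi-squared test. With pooled rate 0.40:

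n per arm = [1.960 × √(2 × 0.40 × 0.60) + 0.842 × √(0.55 × 0.45 + 0.25 × 0.75)]² / 0.30² = (1.358 + 0.555)² / 0.09 = 40.7, so 41.

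Power at 41 per arm is 0.803, and 41 / (1 − 0.18) = 50. The stated size reproduces. It uses an unstratified test and takes no credit for precision from the strata.

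**What study entry means.** The phrase is used for measured GFR (Section 3.2.2), the first SF-36 (Section 3.2.3), the screening renal biopsy (Table 1, footnote 13) and the start of the 26-month clock (Section 1.1). In each case it means entry to RAIN. No section defines it as the time before prior therapy.

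**The two conditions together.** Let b be dFLC before the graded therapy and e be dFLC at RAIN entry, both in mg/L, with the response maintained at entry. PR here means a fall of more than 50% that stops short of VGPR, so e is at least 40.

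| Category | Condition on response | Footnote as written | Result |
|---|---|---|---|
| CR | normal FLC, negative immunofixation | none | classified |
| VGPR | e < 40 | e > 50 | impossible |
| PR, e from 40 to 50 | e < b/2 | e > 50 | impossible |
| PR, e above 50 | e < b/2 | e > 50 | classified; needs b above 100 |

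A patient with e below 40 fails the footnote for PR as well as for VGPR. The literal result is no category at all, not reassignment to PR.

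**Check by enumeration.** Take integer b from 1 to 1000 and integer e from 0 to b − 1. These are counts of combinations, not expected shares of patients, and CR is not modelled.

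- VGPR (e < 40): for b = 1 to 40 there are 1 + 2 + … + 40 = 820 combinations. For b = 41 to 1000 there are 960 × 40 = 38,400. The total is 39,220, of which 0 have e > 50.
- PR (40 ≤ e < b/2): 212,060 combinations. Those with e from 40 to 50 number 11 × 1000 − 2 × (40 + … + 50) = 11,000 − 990 = 10,010, and all fail. The other 202,050 pass.

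**With the condition moved to b > 50.** All 212,060 PR combinations pass, because e of at least 40 with a fall of more than half needs b above 80. Of the VGPR combinations, 38,000 pass and 39,220 − 38,000 = 1,220 fail, namely those with b of 50 or less. Moving the time point removes the contradiction but leaves a residual group that still needs a rule.

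**The case against.** The strongest reply is that the intent is plain. VGPR patients are named as eligible in the synopsis and Section 4.1, and the synopsis and Figure 1 tie response to the most recent treatment. A sensible reader would apply the 50 mg/L condition to the value before that treatment. Every registration form also goes to one medical monitor for eligibility approval before randomization (Sections 3.4.1 and 3.5), so one person sees every case. Both points stand and limit the practical harm. They do not supply the missing rule: the text gives a different time point, and no section says that the monitor checks the stratum separately.

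Four stronger readings are tempting, and the documents do not support them.

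- A reader might infer that a randomization stratum is empty. It is not. The levels are CR/VGPR and PR, and CR patients still fill the first. Only the VGPR category within it cannot be assigned.
- A reader might infer that VGPR patients move to the PR stratum and that the resulting power loss can be calculated. The asterisk is on PR too, so the literal rule leaves them unclassified. The mix of CR, VGPR and PR and its prognostic strength are not in the documents.
- A reader might infer that VGPR patients are ineligible. Criterion 6 lists VGPR explicitly and does not itself cite Appendix 1, although the design statements in the synopsis and Section 3.1 do.
- A reader might infer bias in the primary test. The stratum is set before assignment, so a misplaced patient is equally likely to be in either arm.

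There is one further limit. A patient who reached VGPR and later drifted above 50 mg/L could satisfy the footnote. Appendix 1 lists progression from CR and from PR but none from VGPR, so it does not settle that case.

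**Conclusion.** The footnote is wrong as written, to a minor to moderate degree. With study entry read as it is used elsewhere in the protocol, no patient still meeting VGPR at entry can be classified, and neither can a patient in PR who enters at 40 to 50 mg/L. This is a stated rule that fails when followed, and it defines one of the two randomization factors and the strata of the primary test.

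Type I error is unaffected, and so are the 41 evaluable and 50 randomized per arm. Any effect on power is small: the plan's 0.80 rests on the unstratified test, so even an uninformative hematologic factor would leave power at about the planned level. A more exact figure would need assumptions that the documents do not give. The conclusion rests on two readings: study entry means RAIN entry, and the response is still met at that time.

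**What to change.** 1. In the Appendix 1 footnote, replace the reference to study entry with the dFLC value before the therapy being graded, that is, the most recent line, consistent with the synopsis and Figure 1.
2. Align Section 3.4.1, which says only response to therapy, with that wording.
3. State to which stratum patients who do not meet the 50 mg/L condition are assigned. Without this, those with dFLC of 50 mg/L or less before therapy still have no VGPR or PR category.
4. While blinded, check the hematologic strata already recorded against the corrected definition and document any differences.

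The cost is one footnote, one phrase in Section 3.4.1, one added sentence and a record check. Sample size, alpha and the primary test do not change.

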#### Stratification for Renal Staging

Test	Value	Score
Proteinuria	≤5 g/24 hours	0
	>5g/24 hours	1
eGFR	≥50 mL/min/1.73 m 	0
	<50 mL/min/1.73 m 	1
Total Score		0 = Renal Stage 1 1 = Renal Stage 2 2 = Renal Stage 3

eGFR = estimated glomerular filtration rate.

## Appendix 2 Examples of Highly Effective Contraception Methods

Contraception methods that can achieve a failure rate of <1% per year when used consistently and correctly are considered to be highly effective. Such methods include:

- Combined (estrogen and progestogen containing) hormonal contraception associated with inhibition of ovulation:
  - Oral
  - Intravaginal
  - Transdermal
- Progestogen-only hormonal contraception associated with inhibition of ovulation:
  - Oral
  - Injectable
  - Implantable
- Intrauterine device (IUD)
- Intrauterine hormone-releasing system (IUS)
- Bilateral tubal occlusion
- Vasectomized partner
- Sexual abstinence

 Hormonal contraception may be susceptible to interaction with the Investigational Medicinal Product (IMP), which may reduce the efficacy of the contraception method.

 Contraception methods that in the context of this guidance are considered to have low user dependency.

 Vasectomised partner is a highly effective birth control method provided that partner is the sole sexual partner of the women of childbearing potential (WOCBP) trial participant and that the vasectomised partner has received medical assessment of the surgical success.

 In the context of this guidance sexual abstinence is considered a highly effective method only if defined as refraining from heterosexual intercourse during the entire period of risk associated with the study treatments. The reliability of sexual abstinence needs to be evaluated in relation to the duration of the clinical trial and the preferred and usual lifestyle of the subject.

Source: Clinical Trial Facilitation Group, 2014.

### Appendix 3 Revised International Myeloma Working Group (IMWG) Diagnostic Criteria for Multiple Myeloma

#### *Definition of Multiple Myeloma*

Clonal bone marrow plasma cells > 10% or biopsy-proven bone or extramedullary plasmacytoma\* and any one or more of the following myeloma defining events:

Myeloma defining events:

- Evidence of end organ damage that can be attributed to the underlying plasma cell proliferative disorder, specifically:
- Hypercalcaemia: serum calcium >0.25 mmol/L (>1 mg/dL) higher than the upper limit of normal (ULN) or >2.75 mmol/L (>11 mg/dL)
- Renal insufficiency: creatinine clearance <40 mL per min† or serum creatinine >177 µmol/L (>2 mg/dL) in the absence of amyloidosis
- Anemia: hemoglobin value of >20 g/L below the lower limit of normal, or a hemoglobin value <100 g/L
- Bone lesions: one or more osteolytic lesions on skeletal radiography, computerized tomography (CT), or PET-CT‡
- Any one or more of the following biomarkers of malignancy:
- Clonal bone marrow plasma cell percentage > 60%
- Involved:uninvolved serum free light chain ratio § > 100
- >1 focal lesions > 5mm in size on magnetic resonance imaging (MRI) studies

PET-CT= F-fluorodeoxyglucose positron emission tomography with computed tomography.

\*Clonality should be established by showing kappa/lambda light-chain restriction on flow cytometry, immunohistochemistry, or immunofluorescence. Bone marrow plasma cell percentage should preferably be estimated from a core biopsy specimen; in case of a disparity between the aspirate and core biopsy, the highest value should be used.

†Measured or estimated by validated equations.

‡If bone marrow has less than 10% clonal plasma cells, more than one bone lesion is required to distinguish from solitary plasmacytoma with minimal marrow involvement.

§These values are based on the serum Freelite assay (The Binding Site Group, Birmingham, UK). The involved free light chain must be > 100 mg/L.

#### Appendix 4 Modified Organ Response and Progression Criteria

Organ	Response	Progression
Heart	NT-proBNP response (>30% and >300 ng/L decrease in subjects with baseline NT-proBNP 2650 ng/L) or NYHA class response (2 class decrease in subjects with baseline NYHA class 3 or 4)	NT-proBNP progression (>30% and >300 ng/L increase)
Renal	>30% decrease in proteinuria or drop of proteinuria below 0.5 g/24 hours in the absence of renal progression	>25% decrease in eGFR

Abbreviations: eGFR = estimated glomerular filtration rate; NT-proBNP = N-terminal pro B-type natriuretic peptide; NYHA = New York Heart Association.

